#### 6.3. Exploratory Efficacy Endpoints

Endpoint: The proportion of participants achieving resolution of the target ulcer(s) by Week 24

Population: ITT population as described in Section 4.

Analysis: Descriptive statistics including the number of participants (N) and percentage (%) will be provided by Voxelotor and delayed Voxelotor groups.

Endpoint: Time (in days) to resolution of target ulcer(s) up to Week 24

Population: ITT population as described in Section 4.

Analysis: Number of participants (N) who achieved resolution of target ulcer, median, first quartile (Q1), third quartile (Q3), minimum, and maximum will be provided by Voxelotor and Delayed Voxelotor groups.

Endpoint: Change from Baseline in total surface area of target ulcer(s) over time up to Week 24

Population: ITT population as described in Section 4.

Analysis: Descriptive statistics including the number of participants (N), mean, standard deviation (SD), median, first quartile (Q1), third quartile (Q3), minimum, and maximum will be provided by Voxelotor and Delayed Voxelotor groups.

Endpoint: Correlation between change from Baseline in Hb and target ulcer(s) healing at Week 12 and Week 24.

Population: ITT Population as described in Section 4.

Analysis: The point biserial correlation  $r_{pb}$  will be provided as described in Section 5.2.4 by treatment groups.

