## 8.4.3. Exploratory Endpoints

Exploratory endpoints will be summarized by descriptive statistics. Details will be provided in the statistical analysis plan (SAP).

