## 3.2. Secondary Endpoint(s)

Time (in days) to resolution of target ulcer(s) up to Week 12

Time to resolution of target ulcer(s) is defined as

Date of resolution – Date of randomization +1,

where the date of resolution is defined as the first time of the observed ulcer was resolved. For participants with more than one target ulcer, time to resolution of target

> PFIZER CONFIDENTIAL TMF Doc ID: 98.03 Page 16 of 43

[figure not shown]
ulcer(s) is defined as time to the last target ulcer confirmed resolved. For participants who do not have the last target ulcer confirmed resolved by Week 12 or who are discontinued from study, the time to resolution will be censored.

- Change from baseline in total surface area of target ulcer(s) at Week 12
- Incidence of new ulcers by Week 12

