## 5.2.3. Analyses for Time-to Event Endpoints

Time-to event endpoint will also be summarized using the Kaplan-Meier method (product-limit estimates) and estimated survival curves will be displayed graphically when appropriate. Graphs will describe the number of participants at risk over time. The median, quartiles, and probabilities of an event at particular points in time will be estimated by the Kaplan-Meier method. Confidence intervals for medians and quartiles are based on the Brookmeyer-Crowley method. Confidence intervals for the estimated probability of an event at a particular time point will be generated using the Greenwood formula.

A stratified log-rank test with stratification factors will be performed to test for differences between the voxelotor and placebo treatment groups.

A stratified Cox regression model with treatment group as the covariate will be used to estimate the treatment group hazard ratio (voxelotor vs. placebo) and the corresponding two-sided 95% confidence interval.

Counts and percentages of subjects who experienced the event as well as the counts and percentages of subjects who were censored and the type of censoring (eg, death or missing data) will be reported for each of the treatment groups.

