## Analysis:

The analysis as described in Section 5.2.3 consists of a stratified log-rank test to test the difference in this endpoint between the voxelotor and placebo groups, where the stratification factors are target ulcer size and duration, will be performed and the p-value for log-rank test will be reported. A stratified Cox regression model with the strata

including target ulcer size (categorical) and target ulcer duration (categorical) and the treatment group as the covariate will be used to estimate the hazard ratio (voxelotor vs. placebo) and the corresponding two-sided 95% confidence interval.

Endpoint: Change from baseline in total surface area of target ulcer(s) at Week 12
 Population: ITT Population as described in Section 4.

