# APPENDICES

# Appendix 1. Summary of Efficacy Analyses

Endpoint	Analysis Type	Population	Data Inclusion and Rules for Handling Intercurrent Events and Missing Data	Main Analysis Model
Primary				
The status of participants achieving resolution of the target ulcer(s) by Week 12	Exact CMH test Descriptive summary statistics Subgroup analysis	ITT	Participants who are lost to follow-up or otherwise drop out of the study without confirmation of resolution of all target study ulcer(s) prior to Week 12, will be classified as non- responder.	Exact CMH test with stratification factors of target ulcer size and duration
Secondary				
Time (in days) to resolution of target ulcer(s) up to Week 12	Log-rank and Cox regression model  Descriptive summary statistics  Subgroup analysis	ITT	For participants who do not have the last target ulcer confirmed resolved by Week 12 or who are discontinued from study, the time to resolution will be censored	Kaplan-Meier method (product-limit estimates) and estimated survival curves will be displayed graphically when appropriate. Graphs will describe the number of participants at risk over time. A stratified log-rank test with stratification factors will be performed to test for differences between the voxelotor and placebo treatment groups
Change from baseline in total surface area of target ulcer(s) at Week 12	LS means (95%CI) LS means difference Descriptive summary statistics Subgroup analysis	ITT	NA	MMRM analysis will be used as described in Section 5.2.2.1 with the stratification factors including target ulcer size (categorical) and target ulcer duration (categorical) as covariates and. The p-value for LS means difference (voxelotor vs. placebo) at Week 12 will be provided.

Endpoint	Analysis Type	Population	Data Inclusion and Rules for Handling Intercurrent Events and Missing Data	Main Analysis Model
Incidence of new ulcers by Week 12	Exact CMH test Descriptive summary statistics Subgroup analysis (age group and country)	ITT	NA	Exact CMH test with stratification factors of target ulcer size and duration
Exploratory				
The proportion of participants achieving resolution of the target ulcer(s) by Week 24	Descriptive summary statistics	ITT	NA	Descriptive statistics
Time (in days) to resolution of target ulcer(s) up to Week 24	Descriptive summary statistics	ITT	NA	Descriptive statistics

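### Week 24 time to resolution has no censoring rule and reads as a summary of resolvers only, in conflict with SAP 5.2.3 and the ITT population

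*SAP*

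**What the plan says.** SAP 6.3 defines the analysis of Week 24 time to resolution as "Number of participants (N) who achieved resolution of target ulcer, median, first quartile (Q1), third quartile (Q3), minimum, and maximum", shown for the Voxelotor and Delayed Voxelotor groups. The entry also states "Population: ITT population as described in Section 4", which means all randomised participants. In SAP Appendix 1, the row for "Time (in days) to resolution of target ulcer(s) up to Week 24" names descriptive statistics as the model and marks the column for intercurrent events and missing data as not applicable.

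SAP 5.2.3, under General Methods and with no week attached, says "Time-to event endpoint will also be summarized using the Kaplan-Meier method" and "The median, quartiles, and probabilities of an event at particular points in time will be estimated by the Kaplan-Meier method". It also asks for counts of censored participants by type of censoring, with death as one example.

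The Week 12 version of the endpoint is fully specified. SAP 3.2 has a censoring rule for participants without confirmed resolution: "resolved by Week 12 or who are discontinued from study, the time to resolution will be censored". SAP 6.2 points to the general method: "The analysis as described in Section 5.2.3 consists of a stratified log-rank test".

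Protocol 8.4.3 says "Exploratory endpoints will be summarized by descriptive statistics" and leaves the detail to the SAP.

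**The concern.** Time to resolution is a censored quantity: some ulcers will not have closed by Week 24, and some participants will leave before then. Plain quartiles of the observed times treat it as fully observed and condition on healing. The result describes the speed of those who healed, not the time to healing in the randomised groups.

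The wording of SAP 6.3 points that way. N is the number who resolved, whereas the next endpoint in the same section uses the ordinary number of participants. Minimum and maximum are listed, and these are not among the Kaplan-Meier outputs in 5.2.3. Other entries in 6.3 cite their method section (5.2.4 for correlations, 5.2.2.1 for the PROMIS and VAS models); this one cites none.

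At stake is a reported median that is too short and that says little about how many participants healed.

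**Working it through.** **Plan's own figure.** The documents give no figure for this endpoint. The only design figure is about 90% power for a 35-point difference with 40 per arm at two-sided 5% (Protocol 8.6). The control rate is not legible, so it was swept. Pooled power is lowest at 32.5% versus 67.5%: Φ[(0.35 − 1.96 × 0.1118) / 0.1047] = Φ(1.25) = 89.4%. The figure reproduces. From it, only the 35-point difference and the 40 per arm are used below.

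**Inputs.** Week 24 is study day 168 (SAP Appendix 2.1). Time is taken from randomisation, as in SAP 3.2. The proportion healed by Week 24, p, is not in the documents and is an assumption shown as a range. Healing is assumed exponential.

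**Formulas.**
- Hazard: λ = −ln(1 − p) / 168.
- Median among resolvers: −ln(1 − p/2) / λ.
- Median in all participants, which Kaplan-Meier estimates: ln 2 / λ, reached by Week 24 only if p ≥ 0.5.

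Example, p = 0.5: λ = 0.6931/168 = 0.004126 per day. The resolver-only median is 0.2877/0.004126 = 69.7 days and the true median is 168.0 days.

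| Healed by Week 24 | Resolver-only median (days) | True median (days) | Gap |
|---|---|---|---|
| 40% | 73.4 | not reached | – |
| 50% | 69.7 | 168.0 | 98.3 days, 14.0 weeks |
| 60% | 65.4 | 127.1 | 61.7 days, 8.8 weeks |
| 70% | 60.1 | 96.7 | 36.6 days, 5.2 weeks |
| 80% | 53.3 | 72.4 | 19.1 days, 2.7 weeks |
| 90% | 43.6 | 50.6 | 7.0 days, 1.0 week |

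Between 40% and 60% healed, the resolver-only median moves only from 10.5 to 9.3 weeks. The true median moves from not reached to 18.2 weeks.

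A simulation with 40 per arm and resolution recorded at two-weekly visits gives the same picture. The mean resolver-only median is 76.7 days at 50% and 73.1 days at 60%, against typical Kaplan-Meier medians of 168 and 126 days.

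**Delayed start.** One constant hazard does not describe the Delayed Voxelotor group. A second model lets that group take the voxelotor hazard λv after day 84. The assumed Week 12 control rate runs from 5% to 30%, with 35 points added for voxelotor.

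Example, 20% versus 55%: λv = −ln(0.45)/84 = 0.009506.
- Voxelotor: healed by Week 24 is 1 − 0.45² = 0.7975; resolver-only median −ln(1 − 0.39875)/λv = 54 days; true median 0.6931/λv = 73 days.
- Delayed: healed by Week 24 is 1 − 0.8 × 0.45 = 0.64; resolver-only median 84 − ln(0.68/0.80)/λv = 101 days; true median 84 − ln(0.50/0.80)/λv = 133 days.

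Over the range of control rates, from 5% up to 30%:
- Voxelotor: resolver-only 63 down to 46 days; true 114 down to 55.
- Delayed: resolver-only 115 down to 93 days; true from not reached down to 111.

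Both arms are biased short, but their order is right.

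**Order of the arms.** Constant hazards were simulated with 40 per arm and two-weekly visits. Among trials in which the arm with the lower healing rate had fewer resolvers, that arm still showed the shorter resolver-only median in 31% (60% v 40% healed), 22% (70% v 35%), 35% (50% v 30%) and 16% (80% v 50%).

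**The case against.** The strongest reply is that the SAP nowhere restricts the median to resolvers. The population is ITT, the N could be an event count, and 5.2.3 sets Kaplan-Meier medians and quartiles without a week limit. A programmer who followed 5.2.3 would produce the right output. This stands in part: the resolver-only reading is an inference from the listed statistics, the missing cross-reference and Appendix 1. It does not remove the problem. Even if 5.2.3 governs, the only censoring rule for this endpoint is written for Week 12, so nothing says when an unresolved participant is censored between Weeks 12 and 24.

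Four stronger readings are tempting and not supported.
- A reader might infer that the arm that heals fewer will look faster. In the table the lower healing rate has the longer resolver-only median, and under delayed start the delayed arm's is clearly longer. Reversal can occur by chance, or if the worse arm heals only early, but it is not expected.
- A reader might infer that the median is bound to be far too short. At 80% to 90% healed the gap is about 3 weeks to 1 week.
- A reader might infer that non-healers disappear from the report. SAP 6.3 gives the Week 24 proportion resolved for the same groups, and SAP 6.5.2 gives disposition at Weeks 12 and 24.
- A reader might infer that the May 2024 dosing pause truncated many participants' ulcer follow-up. SAP 2 gives the dates but no count of participants affected before Week 24.

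**Conclusion.** The point holds as an internal conflict and an omission. SAP 6.3 and Appendix 1 describe a plain summary with no Week 24 censoring rule, while 5.2.3 and the ITT population call for a censored analysis.

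If the summary is run as it most naturally reads, the median is too short whenever anyone remains unhealed. The size depends on a healing rate that the documents do not give: about 1 week at 90%, 9 weeks at 60% and 14 weeks at 50%, with the true median not reached below 50%. These figures rest on exponential healing with a constant hazard. So does the finding that resolver-only medians hardly separate 40% from 60% healing; with a delayed start the two arms' resolver-only medians do separate.

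The consequence is limited. The endpoint is exploratory, has no test or decision attached, and is read next to the Week 24 proportion. The Week 12 secondary analysis is unaffected. The change is still worth making because it is small and alters the number reported.

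**What to change.** - **Method:** state in SAP 6.3 and in the Week 24 row of Appendix 1 that the Kaplan-Meier methods of 5.2.3 apply, in the ITT population by randomised arm (Voxelotor, Delayed Voxelotor).
- **Censoring:** censor unresolved participants at their last ulcer assessment up to Week 24, and replace the not-applicable entry in Appendix 1 with this rule.
- **Reporting:** give the Kaplan-Meier median and quartiles, with 'not reached' where that is so, and the percent resolved by Week 24. Add numbers at risk and numbers censored by type, including death, as 5.2.3 already asks.
- **Labelling:** if times among resolvers are also shown, label them as such.
- **Groups:** SAP 2.3.2 defines the open-label efficacy groups by receipt of at least one voxelotor dose, which is narrower than ITT. One sentence should say that this endpoint uses the randomised arms.

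The cost is a few SAP sentences and one table row. Kaplan-Meier summaries are descriptive, so Protocol 8.4.3 needs no change, and the Week 12 output already specified can serve as the template.

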## Endpoint:

- Correlation between change in hemolytic parameter, % reticulocytes and target ulcer(s) healing at Week 12 and Week 24
- Correlation between change in hemolytic parameter, indirect bilirubin and target ulcer(s) healing at Week 12 and Week 24
- Correlation between change in hemolytic parameter, LDH and target ulcer(s) healing at Week 12 and Week 24

Population: ITT Population as described in Section 4.

Analysis: The point biserial correlation  $r_{pb}$  will be provided as described in Section 5.2.4 by treatment groups.

Health-related quality of life (HRQOL) using patient-reported outcome (PRO) measures endpoints:

Endpoint: Change from baseline in PRO HRQOL measures: PROMIS-37 v2.0 Pediatric Profile/PROMIS-43 v2.1 at Week 12 and Week 24.

PROMIS-37 v2.0 Pediatric Profile domains included Physical Function Mobility, Anxiety, Depressive Symptoms, Fatigue, Peer Relationships, Pain Interference and Pain Intensity. PROMIS-43 v2.1 Adult Profile domains included Physical Functioning, Pain Interference, Sleep Disturbance, Fatigue, Anxiety, Depression, Ability to Participate in Social Roles and Activities and Pain Intensity.

The PROMIS-37 v2.0 and PROMIS-43 v2.1 raw score for each domain will be converted to T-score (see Appendix 3) except pain intensity domain in both PROMIS-37 v2.0 and

PROMIS-43 v2.1. All analysis will be based on both raw score and T-score by domain including pain intensity score.

Population: ITT Population as described in Section 4.

## Analysis:

- MMRM analysis as described in Section 5.2.2.1 will be used with target ulcer size
  (categorical) and target ulcer duration (categorical) as covariates and the change from
  baseline in PROMIS domain T-score and raw score at Week 12 as a response
  variable. The p-value for LS means difference (voxelotor vs. placebo) at Week 12
  will be provided for each of domains.
- Descriptive statistics including the number of participants (N), mean, standard deviation (SD), median, first quartile (Q1), third quartile (Q3), minimum, and maximum will be provided by treatment group at Weeks 12 and 24.

Endpoint: Change from baseline in pain level linked to target ulcer(s) assessed by VAS at Week 12 and Week 24

Population: ITT Population as described in Section 4.

## Analysis:

- MMRM analysis as described in Section 5.2.2.1 will be used with target ulcer size
  (categorical) and target ulcer duration (categorical) as covariates and the change from
  baseline in pain level linked to target ulcer(s) assessed by VAS at Week 12 as a
  response variable. The p-value for LS means difference (voxelotor vs. placebo) at
  Week 12 will be provided.
- Descriptive statistics including the number of participants (N), mean, standard deviation (SD), median, first quartile (Q1), third quartile (Q3), minimum, and maximum will be provided by treatment group at Weeks 12 and 24.

Endpoint: Patient Global Impression of Change (PGI-C) score at Week 12 and Week 24 Population: ITT Population as described in Section 4.

Analysis: Descriptive statistics including the percentage of patients for each response will be provided by treatment group at Weeks 12 and 24.

Endpoint: Clinician Global Impression of Change (CGI-C) score at Week 12 and Week 24

Population: ITT Population as described in Section 4.

PFIZER CONFIDENTIAL

Analysis: Descriptive statistics including the number and percentage of patients for each response will be provided by treatment group at Weeks 12 and 24.

#### 6.4. Subset Analyses

## 6.4.1. Subset analysis for efficacy endpoints

Efficacy subgroup analyses will be performed for the primary and secondary efficacy endpoints for the following subsets unless otherwise noted. The forest plots for all subset analysis by endpoint will be provided. P-values will not be provided for any subgroup analysis.

CCI

- Age group with <18 years of age and ≥ 18 years of age

- 4. Country (Nigeria, Kenya and Brazil)

## 6.4.1.1. Primary Endpoint

The proportion of participants achieving resolution of the target ulcer(s) by Week 12

Population: ITT population as described in Section 4

Analysis:

The proportion difference (voxelotor vs. placebo) and 95% CI will be provided by subgroup.

#### 6.4.1.2. Secondary Endpoint

1. Endpoint: Time (in days) to resolution of target ulcer(s) up to Week 12

Population: ITT population as described in Section 4

Analysis:

A Cox regression model with the treatment group as a covariate will be used to estimate the hazard ratio (voxelotor vs. placebo) and the corresponding two-sided 95% CI by subgroup.

Endpoint: Change from baseline in total surface area of target ulcer(s) at Week 12

Population: ITT population as described in Section 4

Analysis:

MMRM analysis as described in Section 5.2.2.1 will be used and the change from baseline in total surface area of target ulcer(s) at Week 12 as a response variable. The LS means difference (voxelotor vs. placebo) with 95% CI for LS mean difference at Week 12 will be provided by subgroup.

PFIZER CONFIDENTIAL TMF Doc ID: 98.03 Page 28 of 43 Endpoint: Incidence of new ulcers by Week 12

Population: ITT population as described in Section 4

## Analysis:

The proportion difference (voxelotor vs. placebo) and 95% CI will be provided by subgroups of age group and country only.

## 6.4.2. Subset analysis for safety endpoints

Safety subgroup analyses will be performed on safety analysis set for SCD-related TEAEs and TESAEs in the randomized treatment period on the following subgroups.

- Malaria
  - a. Subjects with at least one TEAE of Malaria by Week 12 (Yes, No)
  - Subjects with at least one TEAE of Malaria by Week 24 (Yes, No)
- Change from Baseline in Hemoglobin at Week 12 (< 0 g/dL, 0-1 g/dL, >1 g/dL)
- Hemoglobin at Week 12 (< 7 g/dL, >=7 g/dL and <9 g/dL, >=9 g/dL)
- Number of VOCs in the past 12 Months (0 VOCs, >=1 VOCs)
- Number of VOCs in the past 12 Months (1 VOC, >=2 VOCs)
- Country (Nigeria, Kenya, Brazil)

#### 6.5. Baseline and Other Summaries and Analyses

#### 6.5.1. Baseline Summaries

Demographic characteristics will be summarized by treatment group.

Demographic and baseline characteristics such as age, sex, race, and baseline disease characteristics (including number of target leg ulcer(s), total surface area of target leg ulcer(s), and maximum duration of target leg ulcer(s))

- Baseline physical measurements (including height and weight) will be summarized by treatment group.
- 3. The below will be summarized using number (%) of participants by treatment group:
  - Sickle cell disease genotype; and
  - Enrollment site, country and region.

- General medical history will be summarized by treatment group.
- Hydroxyurea use by treatment group.

## 6.5.2. Study Conduct and Participant Disposition

- The below participant population will be summarized by treatment group.
  - ITT Population.
  - Safety-Evaluable Population.
- Participant disposition (eg, discontinuation from study, reason for discontinuation, completed study, and ongoing) will be summarized by treatment group at Week 12 and 24.
- Actual exposure to study drug will be summarized by treatment group at Week 12 and 24.
- Important protocol deviations will be summarized by treatment group.

#### 6.5.3. Concomitant Medications and Nondrug Treatments

The most current World Health Organization (WHO)-Drug coding dictionary will be used to classify concomitant medications.

The number (%) of participants who took each concomitant medication will be provided by treatment group.

## 6.6. Safety Summaries and Analyses

All safety analysis will be performed based on Safety-Evaluable Population as described in Section 4 and Open-Label Treatment Extension Period for Safety as described in Section 2.3.2.

#### 6.6.1. Adverse Events

SCD-related adverse events, defined as MedDRA PTs of sickle cell anaemia with crisis, acute chest syndrome, pneumonia, priapism (male participants only), splenic or hepatic sequestrations, stroke, and osteonecrosis, are included in the summary. Non-SCD-related adverse events are all other adverse events. The TEAEs/TESAEs and treatment-related AEs/SAEs will be displayed by SCD-related and non-SCD-related.

The total number and percentage of subjects with TEAEs will be presented by system organ class and preferred term by treatment group. TEAEs will be presented by severity (CTCAE grade or protocol defined severity). TEAEs will be tabulated presenting the system organ class alphabetically and within each system the preferred term will be presented by treatment group. The total number and percentage of subjects discontinued from study due to AEs will by presented by treatment group.

The frequency of subjects who experience each TEAE or treatment-related AE will be determined as follows: A subject experiencing the same AE multiple times will only be counted once for the preferred term. Similarly, if a subject experiences multiple AEs within the same system organ class, that subject will be counted only once for that system. If changes in the severity of an AE are recorded in the eCRF, only the most severe incidence of the AE will be counted. If a subject experiences multiple occurrences of a TEAE, only the related event or the worst severity (analysis dependent), will be counted for each subject within each system organ class or preferred term for the summaries of treatment-related AEs.

Missing onset dates will be imputed as previously outlined in Section 5.3.2 as required to determine treatment-emergent events. Should an event have a missing severity or relationship to study medication, then the severity or relationship, respectively, will be classified as missing for summary tabulation purposes.

Listings of AEs leading to discontinuation of the study, SAEs and deaths, if any, will be provided.

Listing of all AEs, including AEs occurred after 28 days of the last treatment date.

Deaths and SAEs will be listed and incidence of SAEs (all causalities and treatment-related) will be summarized by system organ class and PT by treatment group.

Serious adverse events (SAEs) will be summarized with counts and percentage. SAE information will be reconciled between the clinical and safety databases prior to the database lock for database release.

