## 6.10. Laboratory Assessments

All laboratory assessments will be performed through a central laboratory. Hematology and serum chemistry will be collected at the Screening visit, Baseline (Day 1), Week 12, Week 24, and EOS/Early Termination. Serum pregnancy test will be performed at the Screening visit, and a urine pregnancy test will be performed at Baseline (Day 1), Week 6, Week 12, Week 18, and Week 24 in female participants who have experienced menarche (see Section 6.10.3 for more information on pregnancy testing). For participants who continue to receive voxelotor beyond 12 weeks in the Open-label Treatment Period (see Section 5.1), hematology and serum chemistry assessments will be conducted every 12 weeks, and urine pregnancy testing will be conducted every 24 weeks. Refer to the SOA (Appendix 1) for the additional details of laboratory tests.

It is the responsibility of the Investigator or designee to assess the clinical significance of all abnormal clinical laboratory values, as defined by the applicable list of normal values on file (ie, local or central laboratory).

For the purpose of this study, a clinically significant laboratory value will be any abnormal result that, in the judgment of the Investigator, is an unexpected or unexplained laboratory value or if medical intervention or corrective action (transfusion, hydration, initiation of antibiotics, or other concomitant medication) is required. Any abnormal values that persist should be followed at the discretion of the Investigator. All clinically significant laboratory value abnormalities are to be recorded as AEs.

Additional and repeat laboratory safety testing for the evaluation of abnormal results and/or AEs during the study may be performed at the discretion of the Investigator or upon request of the Sponsor; it is preferred for the analyses to be conducted by the central laboratory unless medical need necessitates urgent results reporting. Repeat laboratory testing of abnormal potentially clinically significant or clinically significant results for the screening evaluation of the participant may be repeated at the discretion of the Investigator.

Blood specimens collected at the Day 1 visit and Week 12 visit and found to be inadequate for laboratory testing should be redrawn and submitted for laboratory testing within 7 days of the study visit.

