## 2.3.2. Treatment Group and Reporting Period for Analysis

In the study schematic in Figure 1. Study Schema, the study period and treatment groups to be included in the primary and open-label analysis.

Efficacy and Safety: Primary analysis (Randomized Treatment Period):

- Treatment groups:
  - Voxelotor: participants randomized to voxelotor.
  - Placebo: participants randomized to placebo.
- Reporting Period:
  - From Day 1 through Week 12 for subjects who either do not achieve confirmed reepithelialization or achieve it before or at Week 12 visit.
  - From Day 1 through Week 14 for subjects who have the initial skin reepithelialization confirmed at Week 12 and then the 14-week visit will be used to confirm resolution.

Day 1 is defined as the date of randomization. The last day (i.e. Week 12 visit or Week 14) of randomized treatment period is defined as the last day entered on the disposition page for end of randomized treatment period.

Efficacy: Open-label analysis (Open-Label Treatment Period):

- Treatment groups:
  - Voxelotor: participants randomized to voxelotor who received at least one dose of voxelotor.

- Delayed voxelotor: participants randomized to placebo during Randomized Treatment Period (through Week 12) and who received at least one dose of voxelotor on or after the Week 12 visit.
- Total: participants who received at least one dose of voxelotor.

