## Reporting Period:

- After Week 12 (one day after Week 12 visit) through Week 24 for subjects who either
  do not achieve confirmed re-epithelialization or achieved it before or at Week 12
  visit.
- After Week 14 (one day after Week 14 visit) through Week 24 for subjects who have the initial skin re-epithelialization confirmed at Week 12 and then the 14-week visit will be used to confirm resolution.

Safety: Open-label analysis (Open-Label Treatment Extension Period which is combining the entire Open-Label Treatment Period and the Follow-up Period):

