#### 6.6.2. Laboratory Data

All hematology and chemistry laboratory assessments were performed by a central laboratory. Laboratory data will be converted into SI for the analysis. The protocol-specified clinical laboratory (Table 2) findings will be summarized using descriptive statistics by treatment group, without any imputation.

Descriptive statistics will be presented for baseline, each evaluation post baseline, and change from baseline for each post baseline evaluation through 28 days after last dose date.

Laboratory abnormalities will be graded via the Common Terminology Criteria for Adverse Event (CTCAE) or protocol defined severity classification. Laboratory abnormality shifts from baseline will be summarized by treatment group and by reporting periods.

To assess liver injury, a listing of the participants potentially meeting Hy's Law criteria and E-DISH plots will be produced.

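### Open-label safety tables give crude percentages over follow-up of variable, uncapped length, with no person-time rates, so they can mislead in either direction and cannot show whether risk changes with time on drug

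*SAP*

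**What the plan says.** SAP 2.3.2 sets two safety reporting periods. The randomised one runs "From Day 1 through Week 12 for subjects who either do not achieve confirmed reepithelialization" or who achieve it by then. It extends to Week 14 for those whose initial closure is seen at Week 12 and awaits confirmation. The other is the "Open-Label Treatment Extension Period which is combining the entire Open-Label Treatment Period and the Follow-up Period". It starts the day after the Week 12 (or Week 14) visit and ends at end of study. SAP 6.6 bases the safety analyses on the safety-evaluable population and the "Open-Label Treatment Extension Period for Safety as described in Section 2.3.2".

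SAP 6.6.1 gives the measure: "The total number and percentage of subjects with TEAEs will be presented by system organ class and preferred term by treatment group". On counting it says "A subject experiencing the same AE multiple times will only be counted once for the preferred term", and on serious events "Serious adverse events (SAEs) will be summarized with counts and percentage". Deaths are listed. SAP 6.6.1 does not itself say that its tables are made per period; that follows from 2.3.2 and 6.6.

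Three other places fix how long people are observed:
- Protocol 5.1 sets at least 12 weeks of open-label treatment and no maximum.
- SAP 2.3.3 ends the on-treatment period, and so TEAE counting, 28 days after the last dose or at study exit, whichever is earlier.
- SAP 2 records that dosing was paused on 10 May 2024 because of the number of deaths in the study, and that the last visit was on 22 October 2024.

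SAP 6.5.2 summarises exposure only at Weeks 12 and 24.

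For laboratory data, SAP 6.6.2 says "Laboratory abnormality shifts from baseline will be summarized by treatment group and by reporting periods". In participants who continue past Week 24, Protocol 6.10 says "hematology and serum chemistry assessments will be conducted every 12 weeks".

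**The concern.** A percentage of subjects, each counted once, is a cumulative incidence. It has meaning only with a stated length of follow-up. The randomised period has one, nominally 12 weeks. The open-label safety period does not: its length differs between participants and depends on when and how each one left.

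No placebo column runs alongside the open-label tables, so readers will look for a reference. The delayed-voxelotor group supplies one, because the same people were observed first on placebo and then on voxelotor. Setting those percentages side by side compares unequal amounts of observation.

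In a study paused over deaths, a reader will want to know whether event rates change with time on drug. Period percentages without person-time cannot answer that. Nor can the reader rebuild the person-time, since exposure is not summarised after Week 24.

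**Working it through.** **Reproduction.** The documents state no adverse event rate or incidence, so there is no planned figure to reproduce. The percentages below are assumptions. The durations come from the documents or are marked as illustrations.

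**Length of the open-label safety period** (SAP 2.3.2 and 2.3.3; Protocol Appendix 1, footnotes a, d, u and v):
- Moves to an alternative source at Week 24: 24 − 12 = 12 weeks, or 24 − 14 = 10 if the period began after Week 14.
- Leaves at Week 28: 28 − 12 = 16 weeks, or 28 − 14 = 14.
- Continues past Week 24: longer, with no cap. Illustration: 24 weeks of open-label dosing plus 28 days = 28 weeks.
- Cut off by the pause: possibly shorter. Illustration: 4 weeks of open-label dosing before the pause plus 28 days = 8 weeks. The documents do not say how many participants were in this position.

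**Effect of length alone.** Let p be the 12-week percentage and assume a constant hazard λ = −ln(1 − p)/12 per week. The percentage after t weeks is 1 − exp(−λt). For p = 10%, λ = 0.1054/12 = 0.00878.

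| Weeks in period | If 10% in 12 weeks | If 30% in 12 weeks |
|---|---|---|
| 8 | 6.8% | 21.2% |
| 10 | 8.4% | 25.7% |
| 12 | 10.0% | 30.0% |
| 14 | 11.6% | 34.0% |
| 16 | 13.1% | 37.8% |
| 28 | 21.8% | 56.5% |

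**Effect of the denominator.** In SAP 2.3.2 the open-label voxelotor group is everyone randomised to voxelotor who took at least one dose; having entered the open-label period is not required. The delayed group does require an open-label dose. If only a fraction f of the voxelotor denominator entered, the expected percentage is f × [1 − exp(−λt)]. At 16 weeks and p = 10% this equals the 12-week figure when f = 10.0/13.1 = 0.76. For p from 5% to 50% the break-even f runs from about 0.76 to 0.83. Below it, the longer period shows the smaller percentage.

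**Effect of the remedy.** Under a constant hazard, expected first events are 1 − exp(−λt) per person and expected time at risk to first event is [1 − exp(−λt)]/λ. Their ratio is λ whatever the length. For p = 10% that is 0.00878 × 52.18 × 100 = about 46 per 100 person-years in every row of the table; for p = 30% it is about 155. Non-entrants contribute no person-time, so the dilution goes too.

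**The case against.** A reader might infer that open-label incidence must rise simply because that period is longer. The documents do not support this. Participants who move to another source can leave at Week 24, those confirmed at Week 14 start two weeks late, the pause may have truncated TEAE time, and non-entrants can stay in the denominator. The direction is open. That removes the claim of a known upward bias, but not the problem: a percentage whose bias could go either way is no easier to read.

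The controlled comparison also holds up. Both arms have the same nominal 12 weeks, visits and blood draw. The exception is the two extra weeks for participants awaiting confirmation (10% becoming 11.6% in those participants only). No formal comparison across periods is planned. This stands, and it limits the point to the open-label tables.

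A reader might also infer that more blood draws after Week 12 inflate the laboratory shift tables. That needs a rule taking the worst value in the period, and SAP 6.6.2 states none. SAP Appendix 2.1 gives just two post-baseline laboratory windows (Days 2–125 and 126–216), about one per period. If shifts use them, the inflation does not arise. What remains is missing detail: the rule is unstated, and draws after Day 216 have no window.

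Finally, sparser visits after Week 24 need not lose events. Protocol 7 has participants asked at each visit about events since the last one, and Protocol 7.3 requires SAE reports within 24 hours of awareness. This is fair for SAEs. Recall of minor events over 12 weeks may still differ from recall over two, which is one reason to show the two stretches separately.

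**Conclusion.** The point holds for the open-label extension safety tables. Their TEAE and SAE percentages mix risk with length of observation and, in the voxelotor group, with the share who entered the period. The table above shows the possible size. It rests on assumed 12-week percentages, constant risk and full entry; actual rates, follow-up times and numbers entering are not in the documents. Primary efficacy is untouched. This is a worthwhile, inexpensive improvement to the safety reporting, not a flaw in the randomised comparison. The laboratory part is a minor clarification only.

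**What to change.** In SAP 6.6.1, add exposure-adjusted rates of TEAEs, SAEs and deaths for each reporting period: subjects with a first event per person-time at risk, and events per person-time. Take person-time from the on-treatment definition in 2.3.3, so that numerator and denominator stop together; later deaths stay in the listing. Restrict the open-label denominator to participants who entered that period, and print the number. Show the open-label rates up to Week 24 and after it, where the visit schedule changes. Extend the exposure summary in 6.5.2 beyond Week 24.

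Label all of this supplementary, because SAP version 4 (16 December 2024) postdates the last visit (22 October 2024).

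In SAP 6.6.2, state that shift tables use one value per analysis visit, and add laboratory windows after Day 216 to Appendix 2.1.

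The cost is SAP wording and a few tables from dosing and event dates already collected. The tables after Week 24 will be sparse, and a single rate per period still averages over any change in risk within it.
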